## 2. SYNOPSIS

Name of Sponsor/Company: Kallyope, Inc.		
Name of Investigational Product: K-757, K-833		
Name of Active Ingredients: K-757 [REDACTED], K-833 [REDACTED]		
Protocol Number: P006-03	Phase: 2	Country: USA
Title of Study: A Randomized, Placebo-Controlled, Double-Blind 13-Week Study to Evaluate the Safety, Tolerability, and Weight Loss Efficacy of K-757 alone and in Combination with K-833 in Participants who are Obese		
Study center(s): Multi-center study in US		
Studied period (years): 12 months Estimated date first patient enrolled: Oct 2023 Estimated date last patient completed: Jul 2024		Phase of development: 2
Number of participants (planned): Approximately 150 (50 per treatment group)		

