  - characteristic findings of acute pancreatitis on imaging

- If a diagnosis of pancreatitis is confirmed, the subject will be discontinued from blinded K-757/placebo and appropriate treatment and monitoring must be initiated.
- If the investigator and Sponsor agree that acute pancreatitis has been ruled out, all investigational medicinal products (IMP) should be resumed.

The primary reason for discontinuation of trial product must be specified in the source data at the time of discontinuation, and the subject should continue to follow the visit and assessment schedule. The reasons for treatment discontinuations are:

- Adverse event
- Withdrawal of consent
- Lost to follow up
- Pregnancy/Intention to become pregnant
- Death
- Investigator decision
- Significant protocol deviation

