#### 2.2.2 Secondary Endpoints

The study secondary endpoints are:

• Proportion of participants achieving  $\geq$ 5% weight reduction after 13 weeks of treatment

- Change from baseline in body weight (kg) after 13 weeks of treatment
- Proportion of participants who experienced 1 or more treatment-emergent AE
- Proportion of participants who discontinued study medication due to an AE

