#### 5.11 Safety Analyses

The safety measurements include AEs, clinical laboratory assessments, vital signs, 12-lead ECG and physical examination. All summaries will be performed and reported by treatment group using the Safety Analysis Set.

No formal statistical tests or inference will be performed for safety analyses.

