#### **5.11.1.1 Incidence of Adverse Events**

Overall summary tables of TEAEs will be presented showing the number and percentages of subjects with any TEAEs, any TEAEs by maximum severity, any study drug-related TEAEs, treatment-emergent SAEs, any treatment-emergent GI AE, TEAEs leading to study drug withdrawal, and TEAEs with fatal outcome.

The following TEAEs will be summarized by frequency and percentage of subjects by SOC (in alphabetical order) and PT (by decreasing frequency in the K-757 + K-833 arm):

- TEAEs
- TEAEs by maximum severity
- Study drug-related TEAEs
- Treatment-emergent SAEs
- TEAEs leading to study drug withdrawal

If the same AE (preferred term) is reported more than once for the same subject, it will be only counted once in the summary table. For the summary table by severity, if the same AE (preferred term) is reported more than once for the same subject, the maximum severity grade (severe > moderate > mild) will be counted in the summary table.

The following by-subject listings will be provided:

- AEs
- SAEs
- TEAEs leading to study drug withdrawal

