Time from randomization to treatment discontinuation due to any adverse events (weeks) will also be analyzed. For participants who discontinued treatment due to AE, time to treatment discontinuation due to AE is defined as duration of time from date of randomization to the date of treatment discontinuation. Participants who discontinue treatment due to any other reasons will be censored at the date of treatment discontinuation. Participants who complete treatment will be censored at last treatment date. The Kaplan-Meier curves will be displayed by treatment group.

Time from randomization to treatment discontinuation due to any gastrointestinal adverse events (weeks) will also be analyzed. For participants who discontinued treatment due to GI AE, time to treatment discontinuation due to GI AE is defined as duration of time from date of randomization to the date of treatment discontinuation. Participants who discontinue treatment due to any other reasons will be censored at the date of treatment discontinuation. Participants who complete treatment will be censored at last treatment date. The Kaplan-Meier curves will be displayed by treatment group.

A swimmer plot for subjects with GI AEs by preferred term and severity may be provided.

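### The Kaplan-Meier curves for stopping treatment because of an AE or a GI AE censor a competing event, so read as proportions they will generally end slightly above the reported secondary endpoint

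*SAP*

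**What the plan says.** SAP section 5.11.1.2 describes two cause-specific displays: time from randomization to stopping treatment because of any AE, and the same for a GI AE. The rule for both is "Participants who discontinue treatment due to any other reasons will be censored at the date of treatment discontinuation", and "Participants who complete treatment will be censored at last treatment date". The estimator is also the same: "The Kaplan-Meier curves will be displayed by treatment group". In the GI display, the other reasons that are censored include AEs that are not gastrointestinal. The section also plans a curve for stopping treatment for any reason, where this issue does not arise.

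The corresponding crude figure appears twice. SAP section 2.2.2 lists as a secondary endpoint "Proportion of participants who discontinued study medication due to an AE". SAP section 5.11.1.1 tabulates the number and percentage of subjects with "TEAEs leading to study drug withdrawal". On the status of all this, SAP section 5.11 says: "No formal statistical tests or inference will be performed for safety analyses".

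Protocol section 8.3.1.1 requires a primary reason to be recorded for each discontinuation. Its list, which opens "The reasons for treatment discontinuations are", has six entries besides AEs: consent withdrawn, loss to follow-up, pregnancy or planned pregnancy, death, the investigator's decision, and a significant protocol deviation. Neither document mentions competing risks or a cumulative incidence function.

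**The concern.** Censoring suits a participant whose event could still happen but is not observed. A participant who has left treatment for another reason is in a different position, because stopping for an AE is no longer possible. Censoring that participant makes the Kaplan-Meier complement estimate the risk in a setting where nobody stops for any other reason. Even that reading requires other stops to be unrelated to AE risk. This is doubtful for withdrawal of consent in a trial that expects GI intolerance (Protocol section 5.4).

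Tolerability is a secondary objective. A reader is likely to take the end of the AE curve as the percentage who stopped for an AE and compare it with the secondary endpoint. The study report could then show two different figures for what looks like one quantity. If other-reason stops differ between arms, the gap between the two figures would differ as well.

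**Working it through.** **Inputs.**
- From the documents: the censoring rules and estimator above; 50 participants per arm (Protocol Synopsis); 20% dropout (SAP section 3.4).
- Assumed: the 20% is total treatment discontinuation; the AE share of stops is 25% to 75%; other totals run from 10% to 50%; hazards are constant. The documents give neither the AE share nor any arm-specific rate. They also give no figure for these curves, so there is no stated value to reproduce.

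**Formula.** Let D be the proportion stopping for any reason by the end of treatment, and s the share of those stops due to the cause of interest.
- Proportion actually stopping for that cause: D × s.
- Kaplan-Meier complement with other causes censored: 1 − (1 − D)^s.
- Excess: 1 − (1 − D)^s − D × s.

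Example with D = 0.20 and s = 0.5: 1 − 0.80^0.5 = 10.56%, against 0.20 × 0.5 = 10.0%. The excess is 0.56 points, a ratio of 1.056.

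| Total stopping | Excess, AE share 25% | Excess, AE share 50% | Excess, AE share 75% |
|---|---|---|---|
| 10% | 0.10 | 0.13 | 0.10 |
| 20% (plan's dropout) | 0.43 | 0.56 | 0.41 |
| 30% | 1.03 | 1.33 | 0.97 |
| 40% | 1.99 | 2.54 | 1.83 |
| 50% | 3.41 | 4.29 | 3.04 |

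Entries are percentage points.

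**Exact counts in an arm of 50.** These do not depend on constant hazards.
- 5 AE and 5 other stops: the crude figure is 5/50 = 10.0%. If all AE stops come first, the Kaplan-Meier complement is also 10.0%. If all other stops come first, it is 1 − 40/45 = 11.1%.
- 10 AE and 10 other stops: the crude figure is 20.0%. The complement runs from 20.0% to 1 − 30/40 = 25.0%.

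**Simulation, 20,000 arms of 50, constant hazards.** The complement was never below the crude figure.
- 20% total, half AE: mean excess 0.56 points, 95th percentile 1.4, exact agreement in about 3% of arms. With an AE share of 25% or 75%, the two agreed in 11% to 12% of arms.
- 40% total, half AE: mean excess 2.5 points, 95th percentile 4.9, exact agreement in 0.03% of arms.

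**Between arms (illustrative rates).** Suppose two arms each have 15% stopping for AEs, with other stops of 5% and 20%.
- First arm: 1 − 0.80^(15/20) = 15.4%.
- Second arm: 1 − 0.65^(15/35) = 16.9%.

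The curves would show a difference of about 1.5 points where the true proportions are equal.

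**GI curve.** Take 20% total with 10% for AEs, and suppose half the AE stops are GI, so D = 0.20 and s = 0.25. The complement is 5.43% against 5.0%. The excess of 0.43 points is smaller than the 0.56 for all AEs, while the ratio of 1.085 is larger than 1.056. At 25% total with 15% for AEs, the excess is 0.85 points for all AEs, 0.77 if half of them are GI, and 0.90 if 80% are.

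**The case against.** The SAP does not say that the complement of these curves will be reported as a percentage discontinuing. Censoring other causes is a recognised cause-specific display, and the rule is fully specified in advance. The figure that matters, the crude proportion, is reported as a secondary endpoint and again in the AE tables. Reasons for discontinuation are summarised by arm (SAP section 5.2). No test or decision uses the curves. At 50 per arm, one participant is 2 points and the standard error of a 10% proportion is √(0.1 × 0.9 / 50) = 4.2 points. An excess of half a point is therefore less than a third of one participant.

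All of this stands as an argument about importance. It does not remove the problem, because a curve labelled as time to discontinuation due to an AE invites comparison with the endpoint of the same name, and nothing in the SAP warns against it.

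Three stronger readings are tempting, and the documents do not support them.
- A reader might infer that the curve can never match the reported proportion. It does match when no other-reason stop precedes the last AE stop in the arm.
- A reader might infer that the GI curve is overstated by more because more stops are censored. That is true as a ratio. In percentage points it depends on the split and is often smaller.
- A reader might infer that the arms will be distorted differently. They can be, but no arm-specific rates are given.

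**Conclusion.** The point holds as a minor one. Two planned curves treat a competing event as censoring. Read as proportions they are never too low, and they will generally be too high once an other-reason stop comes before an AE stop in the same arm. At the plan's only attrition figure the expected excess is about 0.4 to 0.6 points. At an assumed 40% total it is about 2 to 2.5 points (1.8 at an AE share of 75%). These sizes rest on constant hazards, on an assumed AE share, and on reading the 20% dropout as discontinuation of treatment for all reasons. The direction does not depend on those assumptions.

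The secondary endpoint itself is not affected, since it is a crude proportion. Nor are the all-cause discontinuation curve and the efficacy analyses.

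**What to change.** In SAP section 5.11.1.2, replace the two cause-specific Kaplan-Meier displays with Aalen-Johansen cumulative incidence curves by arm. For the AE curve, the competing event is discontinuation for any reason other than an AE. For the GI curve, it is discontinuation for any other reason, including a non-GI AE. Completers stay censored at their last dose. Keep Kaplan-Meier for discontinuation from any cause.

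Loss to follow-up is itself a recorded reason for stopping, so completion is the only ordinary censoring left. The new curves should therefore end at the crude proportion, apart from any effect of a few days' spread in completers' last dose dates.

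The cost is one or two sentences in the SAP and one SAS option (eventcode in PROC LIFETEST). No new data are needed, because the reason for stopping is already collected. If the sponsor prefers to keep the planned curves, the minimum is a footnote saying that they are cause-specific and should not be read as the proportion discontinuing.

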#### **5.11.2** Clinical laboratory Assessments

The clinical laboratory parameters presented in Table 3 will be assessed at the specific times as outlined in the SOA (Error! Reference source not found.).

Observed values and change from baseline to each visit and time point during on-treatment period (from first dose date up to 2 weeks after the last dose of the study medication) and follow up visit in the clinical laboratory parameters for hematology and clinical chemistry will be summarized by treatment group, using descriptive statistics.

In addition, hematology and clinical chemistry parameters during on-treatment period that meet the Sponsor's pre-defined limits of change as presented in Table 4 will be summarized by treatment group, using frequency and percentage.

Clinical laboratory test parameters for hematology, clinical chemistry and urinalysis along with the associated reference ranges will be listed for individual subjects; abnormal values will be flagged as high or low in the listings. Individual measurements of laboratory tests from hematology, chemistry, and urinalysis that meet the abnormal criteria will be categorized to and listed by not clinical significant and clinical significant. Other clinical laboratory tests, such as,

virus serology, COVID-19 testing, drug screen, pregnancy, and follicle stimulating hormone (FSH) will be presented listings only.

Laboratory data will be summarized or listed in International System of Units (SI).

#### 5.11.3 Vital Signs

Vital signs parameters include systolic and diastolic blood pressure, heart rate, respiratory rate and temperature and are collected at the specified timepoints as outlined in the SOA (Table 2). Blood pressure and heart rate are measured in triplicate.

Descriptive statistics for observed values and the change from baseline in the vital sign parameters will be summarized and presented for each visit and time point by treatment group. For triplicate measurements, the average value will be summarized.

A by-subject listing for the vital signs results will be provided.

#### 5.11.4 Twelve-Lead Electrocardiogram

A triplicate 12-lead ECG will be collected at all specified timepoints as outlined in the SOA (Table 2).

The following parameters will be recorded on the eCRF from the subject's ECG trace: heart rate, QRS interval, PR interval, QT interval, and QT (corrected) (Fredericia's).

Trial sites will calculate the triplicate average QTcF at the screening visit to assess the QTcF exclusion criterion. No other calculation of ECG parameter averages is required for trial sites.

QTcF values and changes from baseline that reach the threshold of pre-defined limits of change as presented in Table 4 will be summarized using the number and percentage of subjects. Average of triplicates will be used to determine if subject meet pre-defined criteria.

ECGs as interpreted by the Investigator to be within normal limits, abnormal but not clinically significant, or abnormal and clinically significant, will be listed.

A by-subject listing for the ECG results will be provided.

#### 5.11.5 Physical Examination

Physical examination (PE) will include assessment of skin, head, ears, eyes, nose, throat, neck, thyroid, lungs, heart, cardiovascular, abdomen, lymph nodes, and musculoskeletal system/extremities, and will be performed at visits as indicated in the SOA (Table 2). Interim PEs will be performed at the discretion of the Investigator, if necessary, to evaluate AEs or clinical laboratory abnormalities.

The shift from baseline to post-baseline visit in the PE result (including normal; abnormal, not clinically significant; abnormal, clinically significant) by body system will be provided.

A by-subject listing for the results of physical examinations will be provided.

#### 5.12 Timing of Analyses

A final analysis will be performed after all subjects complete the study and the database has been locked.

#### 6. Multiplicity

The study tests the primary hypothesis that at least one of the treatment arms is superior to the placebo arm in reducing the body weight calculated as percentage change from baseline after 13 weeks of treatment. Each of the two comparisons between K-757 alone and the combination of K-757+K-833 vs placebo is tested at two-sided alpha of 0.05 with a familywise error rate of 0.10. No other multiplicity adjustment will be performed for secondary and exploratory objectives, which will be tested at two-sided alpha of 0.05.

#### 7. Interim Analysis

No interim analysis is planned for this study.

#### 8 Changes from Pre-specified Analyses in the Protocol

There were no changes in the analyses or definitions planned in the CSP.

# 9 Revision History

Version	Date	Description of Change and/or Rationale	Sections Affected

## 10 Programming Specifications and Considerations

The corresponding programming specifications for variables and programming validation will be provided in a separate document.

## 11 Table, Figure, and Listing (TFL) Shells

The corresponding TFL shells for this SAP will be provided in a separate document.

# APPENDIX 1 Schedule of Events

Table 2 Schedule of Events

Visit Number         1         2         4         5         6         7%         8         9         10         11%         12           Week			14				SOA							
mmber         1         2 d vecks of langes         3 d d sek of langes         4 d sek of langes		Screening Period					Treatn	nent Phas	e by Wee	¥				ET or Post Study F/U
Pay         Affice Res         Week Of It         Week Of It Visit Number	1	2 Rand.	3	4	\$	9	78	%	6	10	118	12	13	Visit Number	1	2 Rand.	3	4	\$	9	78	%	6	10	118	12	13
hay         -28         1         8         15         22         29         36         43         57         71         85           indow (days)         0         ±2         ±2         ±2         ±3         ±3         ±3         ±3         ±3         ±3           strative         Acconsent         X	Week	~4 Weeks	Week 0	Week 1	Week 2	Week 3	Week 4	Week 5	Week 6	Week 8	Week 10	Week 12	EoT 13	Week 15
Findow (days)   0	Study Day	-28	1	8	15	22	29	36	43	57	71	85	76	105
A consent   X	Visit Window (days)	0	0	∓2	∓2	∓2	∓2	∓3	∓3	₹3	±3	₹3	€∓	€∓
ad Consent         X	Administrative													
and Exclusional Story/ applies         X <th< td="">Informed Consent	X													</th<>	Informed Consent	X												
story/substitution         X         X           aphics aphics in comitant and comitant in successment         X         X           1 Assessment         X         X           1 Assessment         X         X           2 Assessment         X         X           3 Ation         X         X           3 Ation         X         X	Inclusion/Exclusion a	X	X											
X	Med History/ Demographics	X												
factivity         X         X           ing         X         X           1 Assessment         X         X           ation         X         X           x         X	Prior/Concomitant Med	x						×						X
Assessment  I ation	Diet and activity counseling		×				X			X				X
1 ation	Clinical Assessment										·			
	Physical Examination	X												X
	Height	×												

Table 2: Schedule of Events (continued)

					SOA	A							
	Screeni ng Period				Tre	Treatment Phase by Week	Phase	by Wea	ek				ET or Post Stu dy F/U
Visit Number	1	2 Ran d.	3	4	5	9	78	8	6	10	118	12	13
Week e	~4 Weeks	We ek 0	We ek 1	We ek 2	We ek 3	We ek 4	We ek 5	We ek 6	We ek 8	We ek	We ek 12	Eo T 13	We ek
Study Day	-28	Ī	8	15	22	50	36	43	57	11	88	92	105
Visit Window (days)	0	0	∓2	∓2	∓7	∓2	#3	#3	#3	±3	±3	±3	#3
Administrative											3	3	
Informed Consent	X												
Inclusion/ Exclusion a	×	X											
Med History/ Demographics	X												
Prior/Concomit ant Med	X						×						×
Diet and activity counseling		X				×			×		12		×
Clinical Assessment	ent												

	ET or Post Stu dy F/U	13	We ek 15	105	#3	×	
		12	Eo T 13	92	#3		
		118	We ek	85	#3		
		10	We ek	71	±3		
	, k	6	We ek 8	57	#3		
	by Wee	90	We ek 6	43	#3		
	Treatment Phase by Week	78	We ek 5	36	#3		
4	atment	9	We ek 4	29	±2		
SOA	Tre	S	We ek 3	22	±2		
		4	We ek 2	15	±2		
		3	We ek 1	8	∓2		
		2 Ran d.	We ek 0	1	0		
	Screeni ng Period	1	~4 Weeks	-28	0	X	X
		Visit Number	Week e	Study Day	Visit Window (days)	Physical Examination	Height

Table 2: Schedule of Events (continued)

					SOA	4							
	Screeni ng Period				Trea	Treatment Phase by Week	Phase	by Wee	ya				or Post Stu dy F/U
Visit Number	1	2 Ran d.	3	4	5	9	78	œ	6	10	118	12	13
Week e	~4 Weeks	We ek 0	We ek 1	We ek 2	We ek 3	We ek 4	We ek 5	We ek 6	We ek 8	We ek 10	We ek 12	Eo T 13	We ek 15
Study Day	-28	1	∞	15	22	29	36	43	57	71	85	92	105
Visit Window (days)	0	0	∓2	±2	±2	±2	#3	#3	#3	±3	±3	±3	#3
Heart Rate/Blood Pressure	X	X	×	×	X	X		X	×	X		X	×
Respiratory Rate/Temperatu re	X	X						-					×
Triplicate 12- lead ECG	X	X		S 5				X				X	
6-ОНА	X												
Laboratory and Safety Assessments	Safety Ass	essmen	ıts										
General Safety Labs: Chemistry b, c	X	×				×			×			X	×
Fasting lipid Panel		X										×	

					SOA	A							H
	Screeni ng Period				Tre	Treatment Phase by Week	Phase	by We	ek				er or Post Stu dy F/U
Visit Number	1	2 Ran d.	3	4	S	9	78	80	6	10	118	12	13
Week	~4 Weeks	We ek 0	We ek 1	We ek 2	We ek 3	We ek 4	We ek 5	We ek 6	We ek 8	We ek 10	We ek 12	Eo T 13	We ek
Study Day	-28	1	8	15	22	29	36	43	57	71	\$8	92	105
Visit Window (days)	0	0	∓2	∓2	∓2	±2	±3	±3	#3	±3	₹3	₹3	#3
General Safety Labs: Hematology	X	X						X				X	×
Liver Function Test			X	X	X			X		X	4		
Urine Drug Screen	X										12		

Table 2: Schedule of Events (continued)

SOA

	Screening Period					Treatn	Treatment Phase by Week	e by Wee	یر				ET or Post Study F/U
Visit Number	1	2 Rand.	3	4	5	9	78	8	6	10	118	12	13
Week e	~4 Weeks	Week 0	Week 1	Week 2	Week 3	Week 4	Week 5	Week 6	Week 8	Week 10	Week 12	EoT 13	Week 15
Study Day	-28	1	8	15	22	59	36	43	21	71	\$8	92	105
Visit Window (days)	0	0	±2	∓2	∓2	∓2	∓3	₹3	₹3	₹7	€∓	£ <del>1</del> 3	∓3
Hepatitis Screen	X												
HIV Screen	X												
hCG Pregnancy Test/FSH Test d	X	X				X			X				X
Thyroid Stimulating Hormone Test	X												
HbA1c Test	X	X										X	
Lipase/Amylase	X	X						X				X	
AE Monitoring	X						X						X
Study Drug Administration and Compliance	ration and C	omplianc	e										
Study Drug Dispensing f		X	×	X	x	×		x	X	X			1
Drug Compliance Check		×	×	×	X	×	×	X	X	×	X	X	

Table 2: Schedule of Events (continued)

						SOA							
	Screening Period					Treatn	Treatment Phase by Week	e by Wee	4				ET or Post Study F/U
Visit Number	1	2 Rand.	3	4	2	9	 18	8	6	10	118	12	13
Week e	~4 Weeks	Week 0	Week 1	Week 2	Week 3	Week 4	Week 5	Week 6	Week 8	Week 10	Week 12	EoT 13	Week 15
Study Day	-28	1	8	15	22	50	36	43	57	71	85	92	105
Visit Window (days)	0	0	7	<del>+</del> 2	2 ∓	7 ∓	€∓	∓3	±3	±3	€∓	₹3	∓3
Efficacy and Other Endpoint Related Assessments	ndpoint Rela	ted Asses	sments										
Blood for K-757/K-833 PK (trough)						×			X			X	
Blood Samples for PD (trough)		X							X			X	2
Body Weight	X	X				X			X			X	X
Other													
Telephone Check g							X				X		
Optional Genetic Blood Sample h		9/										×	

Just prior to Randomization. it will be confirmed that no excluded/prohibited medications are being taken and, in females of child-bearing potential, that the V2/Randomization urine pregnancy test is negative.

Urinalysis at Screening only.

Safety labs will be collected in the fasted state.

Serum hCG at screening and Post-study; urine hCG at randomization and Weeks 5, and 9 for females of childbearing potential. FSH test at screening only for females of non-child bearing potential due to menopause. If screening FSH test is not consistent with menopausal status, subjects may return for a serum pregnancy test and participate under requirements for females of child-bearing potential (contraception and pregnancy testing).

\* Week indicates the duration of treatment completed prior to the visit, not the week in which the visit occurs. For example, the "Week 1" visit is targeted to occur on Day 8 (the first day of the 2nd week of treatment).

- f Titration will occur according to Table 9. On trial site visit days when laboratory safety tests are collected, participants will fast overnight and prior to study drug administration. Dosing will end with the PM dose on Day 91.

  § Telephone calls at Visits 7 and 11 (Day 85) to confirm drug compliance, assess AEs, and concomitant medications.

  h The optional genetic sample may be collected at any time during the study.

  Abbreviations: EoT = end of treatment, ET = end of trial; FU = follow up; hCG = human chorionic gonadotropin

